1. PROTOCOL SYNOPSIS

Study Title: A Phase 1/2a Dose-Escalating Study to Evaluate the Safety, Tolerability and Pharmacokinetic Effects of ARO-ENaC in Normal Healthy Volunteers and Safety, Tolerability and Efficacy in Patients with Cystic Fibrosis

Study Number: AROENAC1001

Phase: Phase 1 First-in-Human, Phase 2a in CF patients

Number of Sites: Normal Healthy Volunteers (NHVs): Single site in New Zealand

Cystic Fibrosis (CF) patients: Multiple sites in New Zealand, Australia, and the United States

Study Treatments:

There will be two study treatments; one active (Test Formulation) and one placebo (Reference Formulation) both administered by inhalation of nebulized solution.

Test Formulation:

The test formulation is active ARO-ENaC to be delivered by nebulized solution. The active pharmaceutical ingredient (API) contained in ARO-ENaC is composed of a synthetic, double-stranded, small interfering RNA (siRNA) duplex conjugated to an $\alpha\beta\beta$ targeting ligand to facilitate pulmonary epithelial cell delivery, formulated in normal saline to be administered by inhalation of nebulized solution.

Reference Formulation:

The reference formulation is placebo (PBO): normal saline (0.9%) administered by inhalation of nebulized solution, volume matched to the corresponding ARO-ENaC dose volume.

Study Objective: The objective of the study is to assess the safety, tolerability, pharmacokinetics of ARO-ENaC in normal healthy volunteers (NHVs) and patients with Cystic Fibrosis (CF).

Primary Endpoint:

- The incidence and frequency of adverse events over time through end of study using escalating multiple doses in NHVs and in CF patients.

Secondary Endpoints:

- Changes from pre-dose baseline in serum electrolytes in NHVs and CF patients as a safety measure.
- Changes from pre-dose baseline in Forced Expiratory Volume (FEV1) in NHVs as a measure of safety.
- Pharmacokinetics of ARO-ENaC in NHVs and in CF patients

Exploratory Endpoints:

- Changes from pre-dose baseline in FEV1 in CF patients
- Changes from pre-dose baseline in lung clearance index (LCI) in CF patients
- Changes from pre-dose baseline in the revised cystic fibrosis questionnaire (CFQ-R) in CF patients
- Rate of pulmonary exacerbations in CF patients receiving ARO-ENaC versus PBO
- Changes from pre-dose baseline in body mass index (BMI) in CF patients
- Plasma metabolite identification in NHVs (reported in a separate report outside of this study)

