- Determination of urinary excretion and metabolite identification in NHVs (reported in a separate report outside of this study)
- Changes from pre-dose baseline to Day 18 in expression of α ENaC using bronchoscopic brush biopsy samples in NHVs
- Changes from pre-dose baseline to Day 18 in expression of α ENaC using bronchoalveolar lavage (BAL) samples in NHVs
- Changes from pre-dose baseline to Day 18 in cytokine levels as well as cell count and differential in BAL fluid in NHVs

Study Population/Patient Number:

Summary of Participant Profile by Cohort:

- Cohorts 1-4: 6 (randomized 4 active: 2 PBO) NHVs per cohort, adult healthy volunteers
- Cohort 5: 12 adult NHVs (randomized 8 active: 4 PBO); only this cohort will undergo bronchoscopies
- Cohorts 2b, 3b: up to 6 (randomized 4 active: 2 PBO) CF adult patients per cohort
- Cohort 4b: up to 12 (randomized 9 active: 3 PBO) CF adult patients with baseline ppFEV1 of > 70%.
- Cohort 6: up to 24 (randomized 18 active: 6 PBO) CF adult patients

NHV subjects will enroll sequentially into a total of 5 cohorts (with 6 subjects in each of cohorts 1-4 and 12 subjects in cohort 5), randomized to receive ARO-ENaC or PBO (4 active: 2 PBO in cohorts 1-4 and 8 active: 4 PBO in cohort 5) in a double blinded fashion. Dose escalation will occur by Data Safety Committee (DSC) vote after review of cumulative safety once all healthy volunteers in the current cohort have completed their Day 21 study visit. There will be no DSC review during cohort 5. Cohort 5 is added to the study for the purpose of obtaining bronchoscopic samples in NHVs.

CF patient cohorts 2b and 3b will each enroll up to 6 patients to receive escalating multiple doses of ARO-ENaC or PBO. CF patient Cohort 4b will enroll up to 12 patients to receive multiple doses of ARO-ENaC or PBO. CF cohort 6 will enroll up to 24 patients to receive multiple doses of ARO-ENaC or PBO. Cohort 6 is included in the study to assess the safety and efficacy of dosing ARO-ENaC on days 1, 15, and 29 (as opposed to all other CF cohorts which dose on days 1/2/3 and 22/23/24).

CF patients not indicated or not treated with CFTR modulators/correctors at baseline or CF patients on a stable regimen (last 2 months) of CFTR modulators/correctors are eligible. CF patients are required to continue their established treatment regimen for the duration of the study without any changes. Sub-group analysis of CF patients will be conducted according to CFTR modulator/corrector use at baseline.

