*#Cohort 6 dose will require 2 nebulizations. Top line indicates total quantity and bottom line indicates quantity per nebulization (in parentheses).

Supply, Preparation, Storage, and Labelling of ARO-ENaC

ARO-ENaC Inhalation is an aqueous solution in a sterile, 10-mL type I glass vial with a fluorocarbon-lined butyl stopper and an orange flip-off seal. Each vial contains a nominal volume of 4.2 mL to provide a full 4.0 mL withdrawable volume.

Strength: 40 mg/mL

Volume: 4.0 mL

Appearance: Clear, colorless to yellow solution

Inactive ingredients: 0.9% saline (0.9% sodium chloride in water)

Shipment and storage: Refrigerated, 2-8 °C

Stability of each lot of ARO-ENaC inhalation is monitored concurrently with the clinical program under both normal and accelerated conditions in accordance with ICH Guidelines.

ARO-ENaC will be prepared, per the Pharmacy Manual, by a pharmacist or qualified staff

member at the clinical sites. The time of preparation for active drug must be documented and tracked to demonstrate administration within prepared drug stability boundaries. Please refer to the Pharmacy Manual for more detailed instructions.

The investigational product vials will be labelled per Good Manufacturing Practice (cGMP)/Good Clinical Practice (cGCP).

Study drug supplies will be stored at clinical sites securely under the appropriate conditions as noted in the Pharmacy Manual.

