12.3. Safety/Tolerability Data

In general, safety analyses will be performed based on Safety Analysis Set, which include all enrolled subjects who receive at least one dose of study drug (placebo or active). Results will be summarized by population (NHV and CF) and cohort. Placebo subjects from each cohort will be pooled by population.

Treatment-emergent AEs will be summarized by System Organ Class (SOC) and Preferred Term (PT), classified from verbatim terms, with MedDRA version 23.0 or later. The incidence and percentage of participants with at least 1 occurrence of a PT will be included, per the most severe grade using a 3-point scale (mild, moderate, severe). The number of events per Preferred Term will also be summarized. Causality (relationship to study treatment) will be summarized separately.

The incidence and frequency of treatment-emergent AEs, SAEs, related AEs, related SAEs and AEs leading to withdrawal, dose modification, or treatment discontinuation will be summarized by population and cohort by SOC and Preferred Terms. All AEs, SAEs will also be summarized in listings. The duration of AEs will be determined and included in listings, along with the action taken and outcome.

Laboratory parameters will be summarized at each scheduled time point using descriptive statistics. The incidence of laboratory abnormalities will be summarized. Results for variables that are not coded will be presented in the listings as “below, within, and above” the normal limits of the laboratory. Pregnancy test results will be listed.

Vital sign measurements will be summarized at each scheduled time point using descriptive statistics. Physical examination findings will be summarized by time point and presented in patient listings.

ECG parameters at each scheduled study visit, changes from baseline and qualitative assessments will be summarized.

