12.6. Pharmacodynamic/Efficacy Data

Descriptive statistics will be performed by scheduled study visit on the following measures of efficacy and pharmacodynamic activity:

- *Spirometry (ppFEV1)*
- *Revised Cystic Fibrosis Questionnaire (respiratory domain)*
- *Lung Clearance Index*
- *Rate of CF Exacerbations*
- *BMI*
- *ENaC mRNA expression from bronchoscopic samples*

Efficacy data for CF patients will be analyzed by cohort. Placebo subjects from each cohort will be pooled. Efficacy analyses will be completed based on Safety Analysis Set, which include all enrolled subjects who receive at least one dose of study drug (placebo or active). CF patients will be analyzed in aggregate and also separately based on CFTR mutation status and based on use or no use of a stable regimen (last 2 months) of CFTR modulators/correctors as well as use or no use of inhaled hypertonic saline.

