## **9. STATISTICAL METHODS OF ANALYSIS**

For all summary tables and figures described in this SAP, NHV Cohorts 1-5 and CF patient Cohorts 2b-4b and 6 will be summarized separately. Subjects will be grouped by dose and dosing regimen within each table and figure, with subjects receiving placebo pooled across cohorts. All data will be combined in listings, which will be sorted by cohort and subject number.

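### Pooling all CF placebo leaves Cohort 6 without a like-for-like control in the TEAE tables; placebo columns by regimen should be added beside the pooled one

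*SAP*

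**What the plan says.** SAP Section 9 sets one layout for all summary tables and figures: "Subjects will be grouped by dose and dosing regimen within each table and figure, with subjects receiving placebo pooled across cohorts". NHV and CF cohorts are summarised separately, and by-subject listings are sorted by cohort. The protocol specifies the same pooling, in Section 12.3 for safety ("Placebo subjects from each cohort will be pooled by population") and in Section 12.6 for efficacy ("Placebo subjects from each cohort will be pooled"). The SAP describes no table that splits CF placebo by cohort, volume or regimen. The table shells are in a companion document that is not available here.

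The protocol synopsis makes placebo saline "volume matched to the corresponding ARO-ENaC dose volume", so each cohort has its own volume-matched control. The inhaled burden differs between cohorts, and Protocol Section 9.1 notes that "Cohort 6 dose will require 2 nebulizations". Planned allocation is "Cohorts 2b, 3b: up to 6 (randomized 4 active: 2 PBO) CF adult patients per cohort", then "Cohort 4b: up to 12 (randomized 9 active: 3 PBO) CF adult patients", then 18 active and 6 placebo in Cohort 6.

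Protocol Section 7.5 and SAP Section 7.3 trigger the primary analysis when Cohort 6 has reached Day 43 and every other cohort has finished. SAP Section 5 counts an AE as treatment-emergent from the first dose onward, with no common cut-off day.

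**The concern.** AE incidence is the primary endpoint, and Cohort 6 receives the highest dose. A within-cohort, volume-matched placebo exists so that an event caused by the inhalation itself is not attributed to the drug. The planned tables separate active subjects by dose and regimen but do not separate the placebo subjects in the same way. A reader comparing Cohort 6 active with the only placebo column sees a difference that could come from the drug, the volume and session length, the number of inhalation days, the lung-function entry rule, or the length of follow-up. Because no formal testing is planned (SAP Section 2.2), readers will draw their conclusions directly from these descriptive tables.

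**Working it through.** **Inputs** (Protocol synopsis, Table 3, Table 4, Section 8.2). Volumes are for the maximum dose; the sponsor may lower the Cohort 6 dose.

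| Cohort | Placebo n | mL per dosing day | Minutes | Dosing days | Total mL | ppFEV1 entry |
|---|---|---|---|---|---|---|
| 2b | 2 | 4.0 | 6-8 | 6 | 24 | 40-90% |
| 3b | 2 | 6.5 | 13-15 | 6 | 39 | 40-90% |
| 4b | 3 | 4.5 | 10-12 | 6 | 27 | above 70% |
| 6 | 6 | 12.2 (2 x 6.1) | 30 (2 x 15) | 3 | 36.6 | 40-90% |

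**1. Reproduce the plan's own figures.** Planned CF patients: 6 + 6 + 12 + 24 = 48. With two extra in each of four cohorts, 48 + 8 = 56, as stated. Volume is dose divided by concentration: 40/10 = 4.0, 65/10 = 6.5, 180/40 = 4.5, 490/40 = 12.25 (stated as 12.2).

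**2. Composition of the pooled column.** 2 + 2 + 3 + 6 = 13, of whom 7 (53.8%) are from 2b-4b. Mean volume per dosing day is (2 x 4.0 + 2 x 6.5 + 3 x 4.5 + 6 x 12.2)/13 = 107.7/13 = 8.3 mL, against 12.2 mL in Cohort 6 active. With the permitted extra patients, the 2b-4b share could run from 7/15 = 46.7% to 13/19 = 68.4%.

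**3. Bias formula.** Let g be the placebo AE proportion under the Cohort 6 regimen minus that under 2b-4b, with no drug effect. Pooled placebo is then 7/13 of the 2b-4b rate plus 6/13 of the Cohort 6 rate. Cohort 6 active minus pooled placebo is +(7/13)g = +0.54g. 2b-4b active minus pooled placebo is -(6/13)g = -0.46g.

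**4. Volume example (assumed rates; the documents give none).** With 10% at 4.0-6.5 mL and 30% at 12.2 mL, pooled placebo is (7 x 10 + 6 x 30)/13 = 19.2%. Cohort 6 is off by +10.8 points and 2b-4b by -9.2. For 5% and 20% the Cohort 6 figure is +8.1; for 10% and 40% it is +16.2; with equal rates it is 0.

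**5. Follow-up example (assumed).** Take a constant hazard giving 50% incidence by Day 113, with Cohort 6 followed only to Day 43. Cohort 6 incidence is 1 - 0.5^(43/113) = 23.2%. Pooled placebo is (7 x 50 + 6 x 23.2)/13 = 37.6%. Cohort 6 active is off by 23.2 - 37.6 = -14.4 points, opposite in sign to step 4. This mismatch belongs to the primary analysis; at the final analysis every cohort is scheduled to Day 113.

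**6. Which visits mix regimens.** Day 37 exists only in 2b-4b and Day 43 only in Cohort 6, so placebo at those visits comes from one regimen. Shared visits are Days 1, 2, 15, 22, 29, 57, 71, 85 and 113. Post-dose spirometry is done on dosing days: 1, 2, 3, 22, 23, 24 in 2b-4b and 1, 15, 29 in Cohort 6. Only Day 1 is common.

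**7. Precision, at 10% and 30%.** Cohort 6 active against matched placebo (18 v 6): SE = sqrt(0.3 x 0.7 x (1/18 + 1/6)) = 21.6 points, with no bias. Against pooled placebo (18 v 13): SE = sqrt(0.21/18 + (7 x 0.09 + 6 x 0.21)/169) = 15.1 points, so root mean squared error = sqrt(10.8² + 15.1²) = 18.6 points. At 10% and 40% the two are nearly equal: 23.1 matched, about 22.7 pooled.

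**The case against.** The strongest defence is that pooling is specified in the protocol, suits a descriptive study with small placebo groups, and gives 13 control subjects rather than 6. All of that stands: this is an analysis choice, not an SAP deviation. Step 7 shows that at the assumed 10% and 30% rates the pooled comparison has the smaller total error despite its bias, so telling readers to use only the n=6 column would not be justified.

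A reader might go further and infer that pooling manufactures a false dose trend. The documents do not support that, for three reasons.
- They give no volume-related AE rate.
- Volume does not follow dose: it is 4.0, 6.5, 4.5 and 12.2 mL for 40, 65, 180 and 490 mg. Each Cohort 6 nebulization is close to the single Cohort 3b one. Total volume is higher in 3b (39 mL) than in Cohort 6 (36.6 mL), and 2b-4b inhale on twice as many days, so g could be negative.
- Any difference between the active columns (0.54g + 0.46g = g) is there under any placebo layout. Pooling only hides the matched placebo that would help explain it.

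A reader might also infer that the matched control is thrown away, or that the efficacy results as a whole are affected. The control is absent from the tables and figures the SAP describes but remains in listings sorted by cohort. Day 43 ppFEV1, the basis of the Cohort 6 sample size, is regimen-specific by schedule. Protocol Section 10.3.7 takes efficacy from the first spirometry of a visit, so an acute post-dose fall would enter the safety data instead.

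**Conclusion.** The point holds as a limit on interpretation. At planned numbers, 7 of the 13 subjects in the only placebo column shown for Cohort 6 differ from it in volume, session length and number of dosing days. Three of the 7 also entered under a stricter ppFEV1 rule, and at the primary analysis all 7 may have much longer follow-up. The TEAE comparison for Cohort 6 cannot attribute a difference, or the absence of one, to the drug. Its error is 7/13 of g, where g is unknown in size and sign. The assumed examples run from +16 points (volume) through zero to -14 points (follow-up), and the two mechanisms could offset each other. The same mixing affects spirometry and LCI at shared visits, including Day 1 post-dose spirometry, but not Day 37 or Day 43. The count of 7 in 13 assumes planned enrolment, and the 12.2 mL assumes the maximum Cohort 6 dose.

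**What to change.** In SAP Section 9, for the CF TEAE tables, and for spirometry and LCI at visits common to both regimens (including Day 1 post-dose spirometry), add two placebo columns: Cohorts 2b-4b (planned n=7) and Cohort 6 (planned n=6). Keep the pooled placebo column. Present Cohort 6 active against both its own placebo and pooled placebo, without directing readers to use only the n=6 column.

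The cost is two extra columns in those outputs. The added columns are small: one event in six is 17 points, and in the 10% and 30% example the SE of the Cohort 6 difference rises from about 15 to about 22 points. The 2b-4b column still mixes 4.0, 4.5 and 6.5 mL, so it is matched on regimen but not on volume. No change to design, data collection or the protocol's pooling rule is needed.

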- **Bronchoscopy:** This is a semi-invasive procedure involving sedation, local anesthesia and insertion of a bronchoscope into the airways. Following insertion of the bronchoscope, bronchoalveolar lavage and bronchial brushings will be performed; notably, no transbronchial biopsies will be taken. Bronchial brushings will be taken from the lung periphery under fluoroscopic visualization of brush location. Complications of bronchoscopy include sore throat, bronchospasm, hypoxemia, laryngospasm or laryngeal injury, fever, and adverse reactions to sedation. The most common adverse event is laryngospasm which occurs in 0.6% of flexible bronoscopies (Pue 1995). More severe complications such as pneumothorax and pulmonary hemorrhage are rare (0.1 to 0.2% for each) and occur more frequently in the setting of transbronchial biopsies, which will not be performed in this study (Pue 1995; Facciolongo 2009). Patient selection has a significant impact on procedural complications and the risks of bronchoscopy in normal healthy volunteers will be lower than in patients with underlying respiratory disease.

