10.3.8. Bronchoscopies

Subjects will be required to fast beginning at midnight the night before the procedure. Following sedation with fentanyl and midazolam (or as per local sedation standards), the bronchoscope will be introduced into the airway and topical anesthesia with xylocaine or lidocaine will be applied to the airway. Subsequently, bronchoalveolar lavage (BAL) and bronchial brushing samples will be obtained. Bronchial brushings will be obtained first.

Bronchial brushings: Small airway brushings will be obtained. The bronchoscope will be wedged into a subsegment of the right lower lobe (see Banerjee 2009 for reference). A sheathed cytology brush will be passed down the working channel of the bronchoscope and then unsheathed under fluoroscopic guidance with the brush tip lying 2-3 cm from the pleural surface. Small airway brushings (\leq 5 brushings) will be collected at this site. The cellular material will be washed off in saline. The liquid will be centrifuged and the cell pellet will be frozen and stored. The cell pellet will be utilized for measurement of α ENaC expression.

BAL: The bronchoscope will be wedged into a subsegment of the right middle lobe and also into a subsegment of the lingula. In each subsegment, 2 x 50 mL aliquots of normal saline will be instilled and then withdrawn via suction (2 aliquots from right middle lobe and 2 aliquots from lingula). Thus, a total of 200 mL of saline will be instilled into the lungs. BAL fluid will be centrifuged and the resultant supernatant will be collected, frozen and stored. BAL cells will be utilized for cell count and differential. BAL supernatant will be used for measurement of cytokine concentrations (including IL-1 β , IL-6, IL-8, and TNF α), as well as for measurement of α ENaC expression in BAL exosomes. An aliquot of BAL fluid will be saved for future research purposes upon the decision of the Sponsor.

Data from the Day 0 bronchoscopy assessment will be used as the baseline value.

Further details on handling of bronchoscopy specimens will be available in the Central Laboratory Manual.

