#### **9.6.6      $\alpha$ ENaC mRNA Expression**

Only NHVs from Cohort 5 will undergo bronchoscopies to evaluate  $\alpha$ ENaC mRNA knockdown. Bronchoscopies will be performed at baseline and on Day 18.

A descriptive statistics summary of  $\alpha$ ENaC mRNA expression will be provided by scheduled visit. Derived changes from baseline will be included.

All bronchoscopy data will be listed by subject.

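### The pooled healthy-volunteer placebo column mixes 4 bronchoscopied subjects with 8 who are not, so procedure adverse events can blur the drug-placebo comparison in opposite directions at low and top dose

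*SAP*

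**What the plan says.** Both documents plan a single placebo column for healthy volunteers. SAP section 9 lays out all summary tables and figures "with subjects receiving placebo pooled across cohorts". Protocol 12.3 has the same rule: "Placebo subjects from each cohort will be pooled by population".

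The synopsis shows who enters that column: "Cohorts 1-4: 6 (randomized 4 active: 2 PBO) NHVs per cohort, adult healthy volunteers", and "Cohort 5: 12 adult NHVs (randomized 8 active: 4 PBO); only this cohort will undergo bronchoscopies". SAP 9.6.6 gives the number of procedures: "Bronchoscopies will be performed at baseline and on Day 18". Protocol 10.3.8 describes sedation, brushing and lavage, and dates the first procedure: "Data from the Day 0 bronchoscopy assessment will be used as the baseline value". Protocol 5.7 lists the risks: "Complications of bronchoscopy include sore throat, bronchospasm, hypoxemia, laryngospasm or laryngeal injury, fever, and adverse reactions to sedation".

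The documents differ on the active groups. SAP section 9 groups them by dose and dosing regimen; protocol 12.3 summarises by cohort. Cohorts 4 and 5 share the Day 1, 2, 3 regimen and the same 180 mg maximum. At equal dose they would therefore be one column of 12 under the SAP but two columns (4 and 8) under the protocol.

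SAP section 5 counts an adverse event as treatment-emergent from the first dose onward.

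**The concern.** The primary endpoint is adverse-event incidence, and the pooled placebo column is its only control. A third of that column has undergone an airway procedure that no active subject in Cohorts 1-3 undergoes and every active subject in Cohort 5 does. No planned active group has the same procedure mix as its comparator.

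The procedure's listed complications (throat, bronchospasm, oxygenation, fever) overlap with the airway effects one would watch for with an inhaled drug. The bias also changes sign between the lower doses and the group that contains Cohort 5. If procedure events are common, they could imitate a dose-response in the respiratory terms that matter most. The adverse-event section of the SAP (9.5.1) plans neither a procedure-related category nor a split by bronchoscopy.

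**Working it through.** **The plan's own figure.** Table 5 (protocol 12.1, SAP 3.2) gives the chance of at least one treatment-emergent event among n subjects as 1 - (1 - p)^n. For n = 8 this gives 0.8322 at p = 0.20 and 0.9424 at p = 0.30, against printed values of 0.83 and 0.94. All 14 cells reproduce. The documents give no figure for the effect of pooling placebo.

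**Composition.**
- Placebo without bronchoscopy: 4 cohorts × 2 = 8.
- Placebo with bronchoscopy: 4 (Cohort 5).
- Bronchoscopied share of the placebo column: 4/12 = 33%.
- Bronchoscopied share of active: 0% in Cohorts 1-3, 8/12 = 67% in a merged 180 mg column, 100% in Cohort 5 alone.

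**Model.** Let b be the background risk of a treatment-emergent event and q the risk that a bronchoscopied subject has at least one procedure event with onset after the first dose. Assume no drug effect and independence.
- Risk with bronchoscopy: pB = 1 - (1 - b)(1 - q), so the added risk is e = pB - b = (1 - b)q.
- Pooled placebo: (8b + 4pB)/12 = b + e/3.
- Cohorts 1-3 minus pooled placebo: -e/3.
- Merged 180 mg column minus pooled placebo: (4b + 8pB)/12 - (b + e/3) = +e/3.
- Cohort 5 alone minus pooled placebo: +2e/3.

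If tables are by cohort, Cohort 4 has the same bias as Cohorts 1-3.

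**Inputs.** b = 30% is the higher of the two planning values in Table 5; using it as a placebo background is my assumption. The only procedure rates in the documents are in protocol 5.7: 0.6% per procedure for laryngospasm and 0.1-0.2% each for pneumothorax and haemorrhage. Larger values of q are assumptions, shown as a range.

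| q | Cohorts 1-3 | Merged 180 mg | Cohort 5 alone |
|---|---|---|---|
| 0.6% | -0.1 | +0.1 | +0.3 |
| 10% | -2.3 | +2.3 | +4.7 |
| 20% | -4.7 | +4.7 | +9.3 |
| 30% | -7.0 | +7.0 | +14.0 |

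Values are percentage points at b = 30%. For example, at q = 20%, e = 0.70 × 0.20 = 0.14, so e/3 = 4.7 points and 2e/3 = 9.3 points. A true 10-point drug excess in Cohorts 1-3 would then show as 10 - 4.7 = 5.3 points. At b = 20% the three biases are slightly larger: -2.7, +2.7 and +5.3 at q = 10%.

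**Which procedure counts.** Protocol 10.3.8 places the first bronchoscopy on Day 0. Its events with onset before dosing enter only the all-adverse-events row of the overall summary, so q reflects mainly Day 18 plus any Day 0 effect that starts after dosing. Table 1.2 as extracted marks the first bronchoscopy under Day 1, which may be an extraction fault.

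**After the change.** Comparing like with like gives b - b = 0 for Cohorts 1-4 and pB - pB = 0 for Cohort 5. The price is precision: the exact upper limit (97.5% one-sided) for zero events, 1 - 0.025^(1/n), is 26.5% for 0/12, 36.9% for 0/8 and 60.2% for 0/4.

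**The case against.** The strongest reply is that the effect may be negligible. Protocol 5.7 calls laryngospasm the most common event, at 0.6%, and expects lower risk in healthy volunteers. Taken at face value, that caps every other complication. Seven named complications at 0.6% plus two at 0.2% give 7 × 0.6 + 2 × 0.2 = 4.6% per procedure, so e = 0.70 × 4.6 = 3.2 points and the bias is about -1 point for Cohorts 1-3 and +2 for Cohort 5 alone. This stands as a limit on what can be asserted. It does not show that the comparator is sound, because no rate is given for sore throat, fever or sedation reactions.

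Second, splitting placebo costs accuracy. At b = 30% and q = 20%, the root mean squared error of the Cohort 5 difference is 24 points against pooled placebo and 30 against its own 4 placebo subjects; for a cohort of 4 active subjects it is 27.1 pooled and 28.1 split. Splitting wins only from about q = 40-45%. This is correct, and it argues against replacing the pooled column. It does not argue against showing the split beside it.

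Third, safeguards exist. There is no hypothesis test, listings are sorted by cohort, and treatment-related events are tabulated separately. These help a careful reader, but they leave the all-cause summary tables unrepaired. Under protocol 11.5.2 an event with another possible explanation can still be graded possibly related.

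A reader might infer something stronger: that procedure events do hide drug events throughout Cohorts 1-4 and do create a false excess in Cohort 5, with both bronchoscopies contributing. The documents do not support that. Under the SAP's grouping at equal dose, Cohort 4 sits in a merged column with a positive bias, so its events are not hidden, and the false excess is half that of Cohort 5 alone. The Day 0 procedure falls largely outside the treatment-emergent tables. The size is conditional on an unstated rate.

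**Conclusion.** The point holds in a conditional form. The pooled placebo column has a different procedure mix from every active group it serves, and post-dose bronchoscopy events can understate the excess over placebo in Cohorts 1-3 and inflate it at the top dose. The inflation falls on Cohort 5 if tables are by cohort. If tables are by dose and regimen and Cohort 5 receives the Cohort 4 dose, it falls at half the size on a merged 180 mg column.

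With no drug effect and a 30% background, the bias runs from under 1 point at the quoted laryngospasm rate to -4.7 / +4.7 / +9.3 points (Cohorts 1-3 / merged / Cohort 5 alone) at an assumed q of 20%. Only the direction and the composition come from the documents; the larger sizes rest on assumed q.

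It would be wrong to infer that healthy-volunteer dose escalation is compromised. Cohort 5 opens only after the Cohort 4 vote, and its dose is no higher than Cohort 4's. What is affected is the final reading of the primary safety endpoint.

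**What to change.** In SAP section 9 and protocol 12.3, keep the pooled healthy-volunteer placebo column (n = 12) and add columns by bronchoscopy status to the healthy-volunteer adverse-event tables:
- placebo from Cohorts 1-4 (n = 8) beside the Cohort 1-4 active groups;
- Cohort 5 placebo (n = 4) beside Cohort 5 active (n = 8), with Cohort 5 active shown separately from Cohort 4 even at equal dose.

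Splitting placebo alone is not enough, because a merged 180 mg column would still mix bronchoscopied and non-bronchoscopied active subjects. For the same reason, reconcile the by-cohort rule in protocol 12.3 with the by-dose-and-regimen rule in SAP section 9.

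The cost is SAP and protocol wording and a few extra columns, with no change to conduct or data collection. The split denominators are small, so state that these columns are to be read beside the pooled one and not in place of it.
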